11.2.1. Safety Analyses

Safety data will be evaluated for vital signs, laboratory outcomes, concomitant medications, ECGs, and AEs. Clinically significant outcomes will be noted. Vital signs and laboratory outcomes will be summarized within each treatment group within all cohorts and the 2 dose groups within Cohort 3. AEs will be coded in the Medical Dictionary for Regulatory Activities; the emphasis will be on treatment-emergent adverse events (TEAEs); the TEAE type, incidence, severity, relationship, onset and resolution time will be displayed descriptively. The incidence rate of AEs and TEAEs will be reported.

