Patients who complete the 52-week Treatment Period and choose not to enroll in optional Extension Period A will be followed for a 12-week Safety Follow-up Period after Day 364 (V15). These patients will have a total of 13 doses. Patients who complete the 52-week Extension Period A and choose not to enroll in optional Extension Period B will be followed for a 12-week Safety Follow-up Period after Day 728 (E14). These patients will have a total of 26 doses. Patients who complete the 52-week Extension Period B will be followed for a 12-week Safety Follow-up Period after Day 1092 (EB14). These patients will have a total of 39 doses.

Based on the results of the prespecified 6-month safety and efficacy interim analyses, any Cohort 3 patients who were randomized to receive low-dose (2 mg/kg) SRK-015 will be re-assigned to receive high-dose (20 mg/kg) SRK-015 after completion of the Treatment Period. Due to the variability in timing of regulatory authority and/or Institutional Review Board/Independent Ethics Committee approvals, the timepoint at which patients who received the low dose (2 mg/kg) will begin receiving the high dose (20 mg/kg) during Extension Period A or B will vary.

A study schema is depicted in Figure 1, Figure 2, and Figure 3.

Figure 1: Study Schematic: Treatment Period

[figure not shown]

Figure 2: Study Schematic: Extension Period A

[figure not shown]
[figure not shown]

Figure 3: Study Schematic: Extension Period B

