2.3.2.2 Treatment-Emergent Adverse Events

Treatment-emergent adverse events (TEAEs) are defined as those AEs satisfying one of the following:

- Occur after the first administration of study drug; or
- Occur prior to the administration of study drug and worsen in severity/grade or relationship to investigational medication after the administration of study drug.

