3 STATISTICAL METHODOLOGY

3.1 General Considerations

The primary analysis will focus on safety and efficacy data up to V15 (Day 364), which will be referred as the 12-month analysis. The interim analysis will focus on safety and efficacy data up to V8 (Day 168). Extension Period analyses where the focus will be safety and efficacy data in

the Extension Period will be carried out separately. The method used in the 12-month analysis will be applied for the Extension Periods and the analyses of the Extension periods will be considered exploratory.

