3.6.1 Adverse Events (AEs)

A summary overview of TEAEs will be provided, which presents the number and percentage of patients in each cohort and dose level from the Safety Population satisfying each of the following categories:

- Any AEs,
- Any SAEs,
- Any TEAEs,
- Any AEs leading to death,
- Any AEs leading to study drug discontinuation,
- Any SAEs leading to death,
- Any SAEs leading to study drug discontinuation,
- Any TEAEs leading to death, and
- Any TEAEs leading to study drug discontinuation,

Adverse events will be coded using the Medical Dictionary for Regulatory Activities (MedDRA) version 23.0 or later. The number and percentage of patients with specific criteria will be summarized by their MedDRA preferred term within system organ class and by treatment within each cohort. These summaries will include patients with the following criteria: TEAEs, SAEs, TEAEs with severity of Grade 3 and above, drug related TEAEs, TEAEs present in 5% or more of patients, and various categories of TEAEs by Time (on or before Week 12 vs. Post Week 12). For patient count summaries, multiple AE events with the same MedDRA coded terms (preferred term and system organ class) from the same patient will only be counted once.

The number and percentage of patients with TEAEs will be summarized by reported maximum severity within each MedDRA preferred term within system organ class and by dose-level within each cohort.

All SAEs will be listed with an indication of whether the SAE was treatment emergent or started prior to treatment. All TEAEs that are reported as leading to study drug discontinuation will be listed. TEAEs leading to death, if applicable, will be listed.

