6 CHANGES FROM PROTOCOL-SPECIFIED STATISTICAL ANALYSES

The statistical analysis section was updated in protocol version 3.0, dated 21 November 2019, and protocol version 4.0, dated 13 November 2020. Subsequent changes in the statistics of the study are detailed here.

The protocol (Section 11.2.1) states, “Vital signs and laboratory outcomes will be evaluated using paired t-tests within cohorts and unpaired t-tests between the 2 dose groups for Cohort 3; corresponding two-sided 95% CIs will be computed as well for the paired and unpaired differences”. In this SAP, descriptive statistics will be used to summarize safety assessments and no statistical testing will be conducted.

The protocol (Section 11.2.2) states, “...proportion and the 95% CI based on Wilson’s method will be reported”. In this SAP, only the proportion will be reported and the 95% CI for proportion will not be calculated.

The protocol (Section 11.2.2) states, “The primary endpoints and other efficacy continuous endpoints will be analyzed using paired t-tests within cohorts and unpaired t-tests between the 2 dose groups for Cohort 3; corresponding 2-sided 95%. CIs will be computed as well for the paired and unpaired differences.” Additionally, the protocol states, “Time to outcome improvement will be assessed using Kaplan-Meier lifetables and a log rank test to compare time to efficacy for Cohort 3 low versus high dose.” In this SAP, descriptive statistics will be used to summarize efficacy and no statistical testing will be conducted.

The protocol (Section 11.4.2) states, “Safety data at all visits and efficacy endpoints at Day 168 (Visit 8) will be included in this analysis.” Due to data cleaning, efforts were focused on up to V10 (Day 224), the interim analysis will include safety data up to V10 (Day 224).

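### The 12-month table of TEAEs up to and after Week 12 gives only patient percentages over 12 and 40 weeks, so it cannot tell longer observation from a rising rate

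*Combined protocol and SAP*

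**What the plan says.** SAP 3.6.1 sets the metric for the adverse event tables: "The number and percentage of patients with specific criteria will be summarized by their MedDRA preferred term within system organ class". One of the listed summaries is "various categories of TEAEs by Time (on or before Week 12 vs. Post Week 12". For patient counts, "multiple AE events with the same MedDRA coded terms (preferred term and system organ class) from the same patient will only be counted once"; the section does not say whether that means once per period or once overall. It specifies no person-time denominator and no equal-length windows, and it does not say who forms the denominator after Week 12.

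SAP 3.1 sets the horizon: "The primary analysis will focus on safety and efficacy data up to V15 (Day 364". SAP 2.3.2.2 opens the TEAE window at first dose ("Occur after the first administration of study drug") and gives no closing date. SAP 3.3.7 derives weeks of exposure for each patient but does not link them to adverse events. SAP 3.1.5 rules out formal testing at the interim and 12-month analyses and gives estimation of event rates as the purpose of the safety work.

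**The concern.** A percentage of patients with an event grows with the length of the window. Two such percentages over 12 and 40 weeks are not on the same scale, and the plan puts them side by side as an early/late contrast.

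Readers are likely to look for a late rise here. Protocol 4.4 gives a serum half-life of 23 to 33 days, so five half-lives take 5 × 23/7 = 16 to 5 × 33/7 = 24 weeks, and drug is still accumulating at Week 12. Every patient receives SRK-015, so no untreated group would show the same pattern. A higher later percentage could be taken for toxicity that builds with exposure when the rate is flat. An event that becomes less frequent could go unnoticed.

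**Working it through.** **Inputs**
- First period: 12 weeks (SAP 3.6.1), taken as 84 days from first dose.
- End of the main analysis: Day 364 (SAP 3.1); 364/7 = 52 weeks. Second period for a completer: 52 − 12 = 40 weeks.
- Event frequency: not in the documents. Assumed 52-week incidence P from 5% to 99%.

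The plan states no figure for this table, so there is none to reproduce.

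**Step 1: constant rate, patients counted once per period.** Hazard h = −ln(1 − P)/52 per week. Share with an event in t weeks = 1 − exp(−ht). Ratio = [1 − exp(−40h)] / [1 − exp(−12h)].

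For P = 50%: h = 0.6931/52 = 0.01333. Early: 1 − exp(−0.160) = 14.8%. Late: 1 − exp(−0.533) = 41.3%. Ratio 2.80.

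**Step 2: constant rate, only the first onset across both periods counted.** Late share = exp(−12h) − exp(−52h). For P = 50%: 0.852 − 0.500 = 35.2%; ratio 2.38.

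| Assumed 52-week incidence | Up to Week 12 | After Week 12, once per period | Ratio | After Week 12, first onset only | Ratio |
|---|---|---|---|---|---|
| 5% | 1.2% | 3.9% | 3.29 | 3.8% | 3.25 |
| 10% | 2.4% | 7.8% | 3.24 | 7.6% | 3.16 |
| 30% | 7.9% | 24.0% | 3.04 | 22.1% | 2.80 |
| 50% | 14.8% | 41.3% | 2.80 | 35.2% | 2.38 |
| 70% | 24.3% | 60.4% | 2.49 | 45.7% | 1.89 |
| 90% | 41.2% | 83.0% | 2.01 | 48.8% | 1.18 |
| 95% | 49.9% | 90.0% | 1.80 | 45.1% | 0.90 |
| 99% | 65.4% | 97.1% | 1.48 | 33.6% | 0.51 |

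Ratios come from unrounded values. The limit for rare events is 40/12 = 3.33. With first-onset counting the ratio falls below 1 above an incidence of about 93%.

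**Step 3: a falling rate.** Suppose 20% have the event by Week 12 and the hazard then halves. Forty weeks at half the hazard equal 20 weeks at the early one, so the later share is 1 − 0.8^(20/12) = 31%. With first-onset counting it is 0.8 × 0.31 = 25%. Both exceed 20%. For rare events the hazard must fall to 12/40 = 0.30 of its early value, a drop of 70%, before the columns look equal.

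**Step 4: person-time measures under a constant rate.**
- Events per time followed: expected events per completer are 12h and 40h; dividing by 12 and 40 weeks gives h both times, ratio 1.0.
- Patients with an event divided by all time followed: with 30% by Week 12, the later share is 1 − 0.7^(40/12) = 69.5%. Then 0.30/12 = 0.0250 and 0.695/40 = 0.0174 per week, ratio 0.70, a false decline. With 10% by Week 12: 0.10/12 = 0.0083 and 0.296/40 = 0.0074, ratio 0.89.
- Patients with an event divided by time up to the first event in the period: expected time is [1 − exp(−ht)]/h, so the quotient is h in each period, ratio 1.0.

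**The case against.** The table is descriptive, no decision rule hangs on it, and its label shows the Week 12 cut. Planned groups are 10 to 20 patients, so most preferred-term cells will be sparse. At a 52-week incidence of 10%, a cohort of 20 expects 20 × 0.024 = 0.5 patients early and 20 × 0.078 = 1.6 late. All of this stands, and it makes the point one of presentation. It does not make the two columns comparable.

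The counting rule also matters. If it means once overall, the artefact shrinks, and for very common terms it reverses. That limits the size stated here and is a reason to settle the rule.

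Four stronger readings are tempting but not supported.
- **That this is the plan's only early/late information.** Protocol 11.2.1 also promises a descriptive display of TEAE onset and resolution times, and SAP 3.6.2 to 3.6.4 summarise laboratory values, vital signs and ECGs by visit.
- **That the SAP dropped a promised person-time rate without listing it in Section 6.** The protocol says "The incidence rate of AEs and TEAEs will be reported" but does not define the term. SAP 3.1.5 itself uses rate for a proportion of patients (1/35). Section 6 also works from protocol versions 3.0 and 4.0, whereas the protocol in hand refers to Version 5.0.
- **That early leavers stay in the later denominator.** SAP 3.6.1 does not state that denominator, and SAP 7 leaves table layouts to separate documents.
- **That the later period is at least 40 weeks throughout.** At the interim, "the interim analysis will include safety data up to V10 (Day 224", which is 224/7 − 12 = 20 weeks after Week 12; a cut at Day 168 would give 12 weeks, equal to the first period. Only patients who decline Extension Period A "will be followed for a 12-week Safety Follow-up Period after Day 364 (V15", so a longer window does not describe the whole cohort. The extension analyses are separate and exploratory, with content still to be agreed (SAP 5.3).

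**Conclusion.** The point holds for the 12-month analysis. As specified, the Week 12 split cannot separate longer observation from a rising rate, and it can hide a falling one. Counted once per period, a flat rate shows as a later percentage 2.0 to 3.3 times the earlier one for terms with a 52-week incidence up to about 90%, and 3.0 or more below about 33%. Above 90% the ratio is under 2.

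This rests on a constant hazard, complete follow-up to Day 364, and assumed incidences, because the documents give none. The consequence is a table open to misreading. No test or planned decision is affected, so this is a cheap improvement and not a correction of an invalid inference.

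**What to change.** In SAP 3.6.1, for the 12-month table:
1. Keep n and % for each period.
2. Add events per 100 patient-years for each period. The denominator is the time each patient was followed within that period; only patients followed beyond Week 12 contribute to the second.
3. If patients with an event per 100 patient-years is also shown, stop each patient's time at the first event in that period. Dividing by all time followed would create the false decline shown in the working.
4. State that the once-only counting rule for patient counts applies within each period.

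The cost is a few lines of SAP text and one or two extra columns. Follow-up time can be split at Week 12 from the dates already used in SAP 3.3.7, and adverse event onset is already recorded. No new data or visits are needed.

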3.6.2 Laboratory Assessments

Descriptive statistics for each parameter will be presented for baseline, each visit, and the change from Baseline. The 95% CI based on the Student's t-distribution for the change from Baseline will be presented.

Frequency tables will be provided to display the number and percentage of patients with laboratory abnormalities after administration of study drug.

3.6.3 Vital Signs

Vital signs include heart rate, blood pressure, and respiratory rate. Vital signs parameters will be summarized using descriptive statistics for each visit. The change from Baseline will also be summarized for each visit along with the 95% CI based on the Student's t-distribution.

3.6.4 Electrocardiograms (ECGs)

Summary statistics for continuous ECG parameters and the change from Baseline, along with the 95% CI based on the Student's t-distribution, will be presented by treatment group for each scheduled visit. Counts and percentages of the overall interpretation of the ECG findings will be

presented by treatment group for each scheduled visit. The 12-Lead Electrocardiogram data will be listed by patient.

3.6.5 Physical Examinations

Physical examination includes an assessment of the following: general appearance, skin, lymph nodes, head-eyes-ears-nose-throat, neck, abdomen, extremities, and the respiratory, cardiovascular, musculoskeletal, and neurologic body systems. Physical examination data will be listed by patient.

4 SAFETY SURVEILLANCE TEAM

An SST will review safety data approximately every 12 weeks, and on an ad hoc basis as needed, throughout the duration of the study (inclusive of Treatment, Extension, and Safety Follow-up Periods) to assess patient safety. Safety reviews prepared by the independent Clinical Research Organization will be provided to a core team comprised of the Scholar Rock Medical Director, the Scholar Rock Product Safety Lead, the Medical Monitor, an independent biostatistician, and a physician not participating as an Investigator in the study. To further assist in the safety assessments, the core SST may request that other individuals such as SMA experts or others within their organizations review the data and participate in the discussions. The SST reviews will not include any efficacy data.

The SST may make recommendations to continue the study with no changes, continue the study with changes to the protocol, terminate the study, or require more data, input, and deliberation prior to making a decision. Criteria for study termination are based on the assessment of safety concerns that may arise during the conduct of the study or from data from the SRK-015 preclinical and clinical program. The study may be discontinued at any time at the Sponsor's discretion, or if the SST determines that further drug exposure would pose an undue risk to patients. The responsibilities and actions of the SST will be governed by a separate SST charter.

5 ANALYSIS TIMING

5.1 Interim Analysis

5.1.1 PK and PD Interim Analysis

Prespecified interim analyses to initially evaluate drug exposure (PK) and target engagement (PD) in patients with SMA will be conducted. For Cohorts 1 and 2, this analysis will be conducted after approximately 4 patients in each cohort have received at least 2 doses of SRK-015. For Cohort 3, this analysis will be conducted after approximately 6 patients have received at least 2 doses of SRK-015. Because individual PK data can reveal treatment assignment, only designated personnel will have access to the PK data and treatment assignments for Cohort 3, and the results will be presented in an aggregated manner. No clinical efficacy endpoints will be examined in this PK and PD interim analysis. Data from multiple cohorts may be combined as necessary. Enrollment will continue while the interim analysis is ongoing. Based on these results, and taking into consideration any available safety data, the cohort-specific dose levels may be adjusted. Any adjustment in dose level will not change the frequency of dosing (i.e., every 4 weeks) and the highest dose will not exceed 30 mg/kg, as tested in the Phase 1 study.

A PK and PD analysis will also be performed at the safety and efficacy interim analysis (see 5.1.2) and the relationship of PK, PD, and efficacy response will be examined. The analysis will be

performed by designated personnel who have access to the PK data and treatment assignments for Cohort 3, and the results will be presented in an aggregated manner.

5.1.2 Safety and Efficacy Interim Analysis

Prespecified interim analyses to evaluate the initial safety and efficacy of SRK-015 in SMA patients was planned in the protocol when all enrolled patients complete V8 (Day 168) or are terminated from the study. Interim analyses were to be performed on the selected efficacy endpoints up to V8 (Day 168), in addition to available selected safety outcomes and PK and PD results (see 5.1.1). Due to COVID-19, some patients delayed or skipped V8 (Day 168). The study sites were given instructions that if the actual visit date is > 56 days but ≤ 84 days from the previous visit then one visit is considered skipped; if >84 days but ≤ 112 days, two visits are considered to be skipped. In addition, some sites kept patient dosing on schedule (no skipping) but did not perform outcome assessment due to PT department closure. If the outcome assessment is skipped regardless of dosing, the site was instructed to perform an outcome assessment at the next visit, which may be unscheduled. Considering these impacts, the safety and efficacy interim analyses will target all patients who have either a V8 (Day 168) measurement or a post V8 (Day 168) visit if V8 (Day 168) is skipped, but will exclude patients with numerous skipped visits.

The following strategies will be adopted to analyze the primary endpoints and to address the COVID-19 impact, where applicable. Because some cohorts may be affected more than others, the strategies may not apply to all cohorts:

- 1) Use the earliest of V8 (Day 168), V9 (Day 196), and V10 (Day 224) data, where available, and for those not having V8-V10 not due to COVID-19, LOCF will be applied.
- 2) For sites closed or patients experiencing travel restrictions/difficulties due to COVID-19 and patients not having V8 (Day 168), V9 (Day 196) and V10 (Day 224) data, those visits will be excluded from the analysis.
- 3) Descriptive analysis will include the earliest of V8/V9/V10.

Descriptive statistics will be used for Efficacy and Safety endpoints at this interim analysis. For continuous efficacy endpoints, the 95% CI of change from Baseline will also be reported.

5.2 Primary / 12-Month Analysis

A 12-month analysis will be performed when all enrolled patients complete V15 (Day 364) or are terminated from the study. The 12-month analysis will be performed on all available efficacy and safety data as described in the above sections of the SAP. Due to COVID-19, some patients delayed or skipped V15 (Day 364).

The database will be frozen before the 12-month analysis is generated and the process for unfreezing any data will be defined in the Data Management Plan. In addition to TFLs, SDTM data and ADaM data along with associated files will be provided. Associated files may include the following: annotated case report forms (CRFs), SDTM specifications, SDTM programs, ADaM specifications, ADaM programs, TFL programs, and CDISC Define packages for both SDTM and ADaM data.

The result of this analysis will be used for the clinical study report.

5.3 Extension Period Analyses

The analyses performed after the 12-month analysis in the Extension periods will be considered exploratory. The timing and content will be pre-approved by the study team before the analyses are performed.

6 CHANGES FROM PROTOCOL-SPECIFIED STATISTICAL ANALYSES

The statistical analysis section was updated in protocol version 3.0, dated 21 November 2019, and protocol version 4.0, dated 13 November 2020. Subsequent changes in the statistics of the study are detailed here.

The protocol (Section 11.2.1) states, “Vital signs and laboratory outcomes will be evaluated using paired t-tests within cohorts and unpaired t-tests between the 2 dose groups for Cohort 3; corresponding two-sided 95% CIs will be computed as well for the paired and unpaired differences”. In this SAP, descriptive statistics will be used to summarize safety assessments and no statistical testing will be conducted.

The protocol (Section 11.2.2) states, “...proportion and the 95% CI based on Wilson’s method will be reported”. In this SAP, only the proportion will be reported and the 95% CI for proportion will not be calculated.

The protocol (Section 11.2.2) states, “The primary endpoints and other efficacy continuous endpoints will be analyzed using paired t-tests within cohorts and unpaired t-tests between the 2 dose groups for Cohort 3; corresponding 2-sided 95%. CIs will be computed as well for the paired and unpaired differences.” Additionally, the protocol states, “Time to outcome improvement will be assessed using Kaplan-Meier lifetables and a log rank test to compare time to efficacy for Cohort 3 low versus high dose.” In this SAP, descriptive statistics will be used to summarize efficacy and no statistical testing will be conducted.

The protocol (Section 11.4.2) states, “Safety data at all visits and efficacy endpoints at Day 168 (Visit 8) will be included in this analysis.” Due to data cleaning, efforts were focused on up to V10 (Day 224), the interim analysis will include safety data up to V10 (Day 224).

